# 5.1. Inclusion Criteria

Participants are eligible to be included in the study only if all of the following criteria apply:

Age

1. Participant must be aged 18 to 55 years, inclusive, at the time of signing the informed consent and of an acceptable age to provide informed consent according to local law.

#### Type of participant and disease characteristics

- 2. Participants with a diagnosis of T1D based on medical history with a fasting C-peptide  $\leq 0.30 \text{ nmol/L} (\leq 300 \text{ pmol/L})$  and the following:
  - a. HbA1c ≤8.5%
  - b. diabetes duration of at least 1 year
  - c. using CSII and stable insulin regimen with a rapid-acting insulin analog for at least 6 months prior to inclusion into the trial
  - d. currently on CSII therapy, with a total insulin dose >0.25 U/kg/day and  $\leq$ 1.2 U/kg/day
  - e. have had no episodes of severe hypoglycemia in the past 6 months (severe hypoglycemia is defined as having neurological symptoms consistent with neuroglycopenia and required assistance in treatment by a second party)
  - f. have clinical laboratory test results within normal reference range with acceptable deviations that are judged to be not clinically significant by the investigator.
  - g. a peak VO2 of  $\geq$ 35 for males and  $\geq$ 32 for females
  - h. able to undergo at least 1 hour of moderate-intensity treadmill exercise (walking or jogging depending on baseline fitness)
  - i. exercise regularly ( $\geq$ 3 times per week of moderate or vigorous exercise)
  - j. are using a personal CGM or FGM to self-monitor glucose
    - i. are capable of, and willing, to do the following: Perform 4-point SMBG, prior to designated visits (participants using a personal CGM or FGM
    - ii. keep records in participant study diaries required by this protocol

#### Weight

3. Participants with a body mass index within the range 18.5 to 29.0 kg/m^2 (inclusive).

#### Sex and contraceptive/barrier requirements

4. Male and female

Contraceptive use by participants should be consistent with local regulations regarding the methods of contraception for those participating in clinical studies.

a. Male participants:

Males may participate in this trial.

No male contraception is required except in compliance with specific local government study requirements.

b. Female participants:

1. Women of childbearing potential may participate in this trial as long as they follow the contraception guidance outlined in Section 10.4.

2. Women not of childbearing potential may participate in this trial.

Please refer to Appendix 4 (Section 10.4) for definitions and additional guidance related to contraception

#### **Informed consent**

5. Participants whom are capable of giving signed informed consent as described in Appendix 1 (Section 10.1), which includes compliance with the requirements and restrictions listed in the ICF and in this protocol.

#### **Other inclusions**

- 6. Participants who have venous access sufficient to allow for blood sampling as per protocol.
- 7. Participants who are reliable and willing to make themselves available for the duration of the study and are willing to follow study procedures.

# 5.2. Exclusion Criteria

Participants are excluded from the study if any of the following criteria apply:

#### **Medical conditions**

- 8. Participants who are lactating.
- 9. Women of childbearing potential who are not following contraception guidance as mentioned in Section 10.4.
- 10. Participants who have known allergies to study intervention, related compounds, or any components of the formulation
- 11. Participants who have an abnormal blood pressure and/or pulse rate as determined by the investigator.

- 12. Participants who have significant previous or current history of comorbidities capable of significantly altering the absorption, metabolism, or elimination of drugs; of constituting a risk when taking the investigational product; or of interfering with the interpretation of data
- 13. Participants who have a current psychiatric disorder that may prevent them from being compliant with study procedures
- 14. Participants who regularly use known drugs of abuse or show positive findings on drug screening.
- 15. Participants who show evidence of human immunodeficiency virus infection and/or positive human immunodeficiency virus antibodies.
- 16. Participants who have spontaneously cleared hepatitis C virus infection, defined as
  - a. a positive hepatitis C virus antibody test and
  - b. a negative hepatitis C virus RNA test.
- 17. Participants who show evidence of possible chronic or active hepatitis B, including hepatitis B core antibody and hepatitis B surface antigen positivity or both.
- 18. Participants who have donated blood of more than 500 mL within the previous 4 weeks of study screening.
- 19. Participants with clinically significant cardiac or pulmonary disease (e.g., angina, clinically significant cardiac arrhythmias, exercise-induced bronchospasm that requires bronchodilators or would preclude completing exercise).
- 20. Participants with severe neuropathy, in particular autonomic neuropathy, as judged by the investigator.
- 21. Participants who have had lymphoma, leukemia, or any malignancy within the past 5 years except for basal cell or squamous epithelial carcinomas of the skin that have been resected with no evidence of metastatic disease for 3 years.

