# 5. Study Population

Eligibility of participants for enrollment in the study will be based on the results of screening medical history, physical examination, vital signs, clinical laboratory tests, diabetes device downloads, and ECG. The nature of any conditions present at the time of the physical examination and any preexisting conditions will be documented.

The inclusion and exclusion criteria used to determine eligibility should be applied at screening only unless otherwise specified, and not continuously throughout the trial.

Prospective approval of protocol deviations to recruitment and enrollment criteria, also known as protocol waivers or exemptions, is not permitted.

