#### **Other exclusions**

- 27. Participants who have an average weekly alcohol intake that exceeds 21 units per week (males aged  $\leq$ 55 years) and 14 units per week (females).
- 28. Participants who are unwilling to stop alcohol consumption for 24 hours prior to each study treatment and during the study treatment periods.
- 29. Participants who smoke more than 10 cigarettes per day or the equivalent including electronic cigarettes or are unable to abide by CRU smoking restrictions.
- 30. Participants who are unwilling to comply with the dietary restrictions required for this study.
- 31. Participants who in the opinion of the investigator or sponsor, are unsuitable for inclusion in the study.
- 32. Participants who do not achieve the optimal basal rates, at the discretion of the investigator, at second evaluation of basal rate optimization visits.
- 33. Individuals following a very low-carbohydrate diet, defined as ≤50 g per day of carbohydrates or ≤10% carbohydrates as a proportion of calories

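### Exclusion criterion 16 bars only cleared hepatitis C, does not reach active infection, and cannot be assessed from the listed screening tests

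*Protocol*

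**What the plan says.** Under Protocol Section 5.2, meeting any one listed criterion excludes a person. Three consecutive criteria concern viral infection:

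- Criterion 15: "Participants who show evidence of human immunodeficiency virus infection and/or positive human immunodeficiency virus antibodies".
- Criterion 16: "Participants who have spontaneously cleared hepatitis C virus infection, defined as" two conditions joined by *and*. The first is a positive antibody test; the second is "a negative hepatitis C virus RNA test".
- Criterion 17: "Participants who show evidence of possible chronic or active hepatitis B", with antibody and antigen markers given as examples.

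Three general clauses could also apply to a person with hepatitis C:

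- Inclusion 2f requires normal screening laboratory results, with "acceptable deviations that are judged to be not clinically significant by the investigator".
- Exclusion 12 covers significant comorbidity, including conditions capable "of constituting a risk when taking the investigational product".
- Exclusion 31 covers "Participants who in the opinion of the investigator or sponsor, are unsuitable for inclusion in the study".

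Section 5 adds: "Prospective approval of protocol deviations to recruitment and enrollment criteria, also known as protocol waivers or exemptions, is not permitted". Appendix 2 (Section 10.2) lists hepatitis C antibody among the screening tests. It lists no hepatitis C RNA test, although the investigator may order additional tests. An antibody result from the 6 months before screening may be used instead of a new one.

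**The concern.** The neighbouring criteria cover current HIV infection and active hepatitis B. Criterion 16 does not cover current hepatitis C. A person with no detectable virus meets a firm exclusion that cannot be waived. A person with detectable virus falls outside that criterion and is left to clauses that depend on judgment. The firm rule is therefore attached to the lower-risk status.

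The criterion is also hard to operate. One of its two conditions needs a result that the listed panel does not produce.

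What is at stake is participant safety and consistent screening decisions. Screening is the main laboratory check: SAP Section 9.6.4 says clinical laboratory data are collected only then, and Protocol Section 7.1.1 sets no liver chemistry stopping criteria.

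**Working it through.** No arithmetic applies, and the plan gives no figure to reproduce. The check is a logic table. It takes criterion 16 as written (antibody positive **and** RNA negative) and compares it, for each status, with a rule that excludes any positive antibody test.

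| Antibody | RNA | Status | Criterion 16 as written | Antibody rule |
|---|---|---|---|---|
| + | − | cleared without treatment | excluded | excluded |
| + | − | cured by treatment | unclear | excluded |
| + | + | active infection | not reached (second condition fails) | excluded |
| + | not tested | unknown | not established | excluded |
| − | + | early infection | not reached (first condition fails) | not reached |
| − | − | no evidence of infection | not reached | not reached |

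1. **Active infection.** Row three is the main gap: a positive RNA result takes the person outside criterion 16. Sections 5.1, 5.2 and 5.2.1 contain no other criterion that names hepatitis C, and neither amendment summary has an entry for criterion 16.

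2. **People cured by treatment.** Row two is unclear because the stem and the definition differ. The stem requires spontaneous clearance, which a treated person did not have. The two laboratory conditions describe that person exactly.

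3. **Assessability.** Using only the Appendix 2 tests, every antibody-positive candidate stays in row four. Moving anyone to another row needs an RNA test that the panel does not list.

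4. **General clauses.** The antibody test is in the screening safety laboratory table, so I read inclusion 2f as covering it. A positive result then disqualifies unless the investigator judges it not clinically significant. Exclusions 12 and 31 can also keep an active case out. None of the three names hepatitis C, and each turns on judgment.

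**The case against.** The strongest reply is that active hepatitis C is already handled. The screening panel includes antibody, liver enzymes, bilirubin and albumin, and Section 8 requires all screening evaluations to be completed and reviewed. Under 2f, a positive antibody result bars entry by default. This largely stands. A reader might infer from criterion 16 alone that active infection can enter freely, and the documents do not support that. What remains is that the outcome depends on a judgment, where HIV and hepatitis B have named criteria.

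A reader might also infer that the criterion is inverted, meaning that the sponsor intended to bar active infection and admit cleared infection. Criteria 15 and 17 make a slip plausible, but the documents do not state the intent of criterion 16. The sponsor may have meant to bar both. Mis-specified is as far as the text goes.

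Third, the documents show no mechanism by which active hepatitis C would harm a participant here. Both products are marketed insulin lispro formulations, given in four short supervised stays. This also stands, and it keeps the point minor.

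Finally, the antibody rule has costs of its own, set out under the fix.

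**Conclusion.** The point holds as a minor drafting defect in eligibility. Criterion 16 bars antibody-positive, RNA-negative people, does not reach antibody-positive, RNA-positive people, and cannot be assessed from the listed panel. Active infection is kept out only by 2f, which is a default bar open to investigator judgment, and by exclusions 12 and 31.

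The literal reading is certain. The size is an assumption, because the documents give no count of affected candidates. With about 32 participants planned (SAP Section 7) at a single center (Protocol Section 4.1), I assume few or none. The sample size, alpha level and primary analysis are unchanged. Any gain is a small one in safety and consistency: a firm rule in place of case-by-case judgment.

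**What to change.** Reword criterion 16 to: *Participants who have a positive hepatitis C virus antibody test.* This parallels the antibody wording of criterion 15 and uses a test already on the panel, so it adds no test or visit.

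The amendment should state the effects. People who cleared the infection stay excluded. Antibody-positive people with positive or unknown RNA become excluded by a named rule. People cured by treatment may be newly excluded, if the word *spontaneously* in the present stem governs. Antibody-negative early infection is still not detected.

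If the sponsor wants to admit cleared and cured people, the alternative is to exclude RNA-positive infection and add RNA testing of antibody-positive candidates to Appendix 2. That costs an extra test.

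Either change needs IRB/IEC approval under Section 10.1.1, and health authority approval if it is deemed substantial. It could be bundled with another amendment.

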#### **Prior/concomitant therapy**

- 22. Participants with current use of any glucose-lowering agents other than insulin that might impact outcome measures:
  - a. any agents that affect hepatic glucose production, including all beta-adrenergic agonists or antagonists, all xanthine derivatives
  - b. beta blockers
  - c. any noninsulin diabetes therapy, (i.e., pramlintide. etc.).
- 23. Participants who intend to use over-the-counter or prescription medication including herbal medications and traditional medications that affect blood glucose level or the body's sensitivity to insulin, or that promote weight loss within 14 days prior to dosing. Specific medications listed in Section 6.8, Concomitant Medications, may be allowed.
- 24. Participants who intend to use acetaminophen **CC** during the basal rate optimization, assessment day, or study periods.

#### Prior/concurrent clinical study experience

25. Participants who have previously completed or withdrawn from this study.

26. Participants who have participated, within the past 30 days, in a clinical study involving an investigational product. If the previous investigational product has a long half-life, 5 half-lives or 30 days (whichever is longer) should have passed.

#### **Other exclusions**

- 27. Participants who have an average weekly alcohol intake that exceeds 21 units per week (males aged  $\leq$ 55 years) and 14 units per week (females).
- 28. Participants who are unwilling to stop alcohol consumption for 24 hours prior to each study treatment and during the study treatment periods.
- 29. Participants who smoke more than 10 cigarettes per day or the equivalent including electronic cigarettes or are unable to abide by CRU smoking restrictions.
- 30. Participants who are unwilling to comply with the dietary restrictions required for this study.
- 31. Participants who in the opinion of the investigator or sponsor, are unsuitable for inclusion in the study.
- 32. Participants who do not achieve the optimal basal rates, at the discretion of the investigator, at second evaluation of basal rate optimization visits.
- 33. Individuals following a very low-carbohydrate diet, defined as ≤50 g per day of carbohydrates or ≤10% carbohydrates as a proportion of calories

#### 5.2.1. Additional criteria for study treatment periods

For participants who fulfill 1 or more of the following criteria prior to the in-house periods, the in-house period can be rescheduled 1 to 14 days later. For the assessment day, rescheduling will be within the allowable time window mentioned in the SoA. Each of the study treatment periods can only be rescheduled once.

- a. consumption of alcohol within 24 hours prior to each in-house period, or a positive result for the alcohol or drug test
- b. consumption of coffee, tea, chocolate, cola, energy drinks and/or energy drinks containing methylxanthine within 8 hours prior to start of dosing with study intervention during each in-house period
- c. strenuous exercise within the past 24 hours prior to each in-house period.
- d. any medical condition or AE that could interfere with glucose metabolism, as judged by the investigator
- e. any use of prescription or nonprescription medication as per exclusion criteria 23 and 24
- f. hypoglycemia CCI posing a safety problem as judged by the investigator, or
- g. participant is unable to obtain glucose range (CC) prior to initiation of exercise assessment.

## 5.3. Lifestyle Considerations

Throughout the study, participants must adhere to lifestyle restrictions as outlined by the CRU and in the study procedures. Participants will be assessed for compliance with requirements before continuing in the study. When not resident in the CRU, participants may resume their regular diet.

#### 5.3.1. Meals and Dietary Restrictions

- While resident at the CRU, participants may not consume any food or caloric drinks other than that provided by the CRU. While not resident at the CRU, participants may resume their regular diet.
- The time of meal start and completion, the total calories, and grams of carbohydrates consumed in the MMTT (Section 5.3.1.1), and the standardized meals (Section 5.3.1.3) during the assessment day and Day 1 of in-house period will be captured in the study eCRF.

## 5.3.1.1. Mixed Meal Tolerance Test

On assessment day and on Day 1 of in-house periods, a dinner liquid MMTT will be administered 1 hour after the exercise assessment as mentioned in Sections 4.1.2 and 4.1.3 and as outlined in Section 1.3. The standardized liquid test meal will use **CC** 

The macronutrient composition of the meal will contain approximately 50 g of carbohydrates, approximately CCI of protein, and approximately CCI of fat. Participants will be fasted, except for water, for 4 hours before each test meal and are required to consume the MMTT within approximately CCI approximately CCI and the MMTT meals will be kept consistent across the assessments in the study. Participants will not be allowed to consume water for CCI after dosing apart from fluid provided with the meal. However, water may be consumed freely after post-dose.

## 5.3.1.2. Standardized Lunch Meal

On assessment day and on Day 1 of in-house periods, a standardized lunch will be administered prior to the exercise assessment as mentioned in Sections 4.1.2 and 4.1.3 and as outlined in Section 1.3. The macronutrient composition of the lunch should be targeted to provide approximately CC of the calories from carbohydrate CC of the calories from fat, and CC of the calories from protein. The standardized lunch for each participant will be kept consistent for all assessment periods. Participants will consume the meal within approximately CC.

## 5.3.1.3. Standardized Breakfast and Dinner Meals

Participants will be provided individualized standardized meals during the in-house periods and assessment day, as outlined in Section 1.3. The macronutrient composition of the meals should be targeted to provide approximately **CO** of the calories from carbohydrate, **CO** of the calories from fat, and **CO** of the calories from protein. Participants will consume each meal within approximately **CO** minutes. Breakfast and dinner meals for each participant during the in-house periods will be kept consistent with regard to calories and nutrient content.

#### 5.3.1.4. Snacks

Snacks with **CCI** of carbohydrates are allowed at bedtime during in-house periods unless otherwise specified in the protocol.

#### 5.3.2. Substance Use: Caffeine, Alcohol, and Tobacco

- During the in-house period, participants will abstain from ingesting caffeine- or xanthine-containing products (e.g., coffee, tea, cola drinks, and chocolate) for 8 hours before the start of dosing with study intervention until after collection of the final PK sample, excluding the MMTT when **CC** Plus may be given.
- During each dosing session, participants will abstain from alcohol for 24 hours before the start of dosing until after collection of the final PK sample.
- Participants who use tobacco products will be instructed to abide by the smoking restrictions while they are in the CRU.

## **5.3.3.** Activity

Participants will be encouraged to maintain their regular exercise and insulin regimen adaptation related to exercise during the outpatient period; however, they should not undertake vigorous or prolonged exercise at least 24 hours before each dosing day at the CRU.

Participants will be instructed to perform exercise on assessment day and on Day 1 of in-house periods as mentioned in Sections 4.1.2 and 4.1.3. On Day 1, a pre-exercise glucose target of

4.1.3. will need to be achieved CCI prior to exercise as mentioned in Section

# 5.4. Screen Failures

A screen failure occurs when a participant who consents to participate in the clinical study is not subsequently randomly assigned to study intervention.

Individuals who do not meet the criteria for participation in this study (screen failure) may be rescreened only once. Rescreened participants will be required to undergo all screening assessments and procedures. The interval between rescreening should be at least 28 days. Each time rescreening is performed, a new informed consent form (see Section 10.1.2 for details) must be signed and participants will be assigned a new identification number.

# 6. Study Intervention(s) and Concomitant Therapy

Study intervention is defined as any investigational intervention(s), marketed product(s), placebo, or medical device(s) intended to be administered to/used by a study participant according to the study protocol.

# 6.1. Study Intervention(s) Administered

Intervention Name	Lyumjev TM	Humalog ®
Туре	Drug	Drug
Dose Formulation	10-mL vial	10-mL vial
Unit Dose Strength(s)	100 U/mL	100 U/mL
Dosage Level(s)	Basal and bolus infusion based on individual needs	Basal and bolus infusion based on individual needs
Route of Administration	Subcutaneous infusion via CSII	Subcutaneous infusion via CSII
Use	Experimental Active comparator	
IMP and NIMP	IMP	IMP
Sourcing	Provided centrally by the sponsor	Provided centrally by the sponsor
Packaging and Labeling	The study intervention will be provided to the CRU in unblinded vials. All clinical study materials provided to the investigator will be stored in a secure place and allocated and dispensed by appropriately trained staff. Detailed records of the amounts of the study intervention received, dispensed, and remaining at the end of the study will be maintained. The study intervention will be	The study intervention will be provided to the CRU in unblinded vials. All clinical study materials provided to the investigator will be stored in a secure place and allocated and dispensed by appropriately trained staff. Detailed records of the amounts of the study intervention received, dispensed, and remaining at the end of the study will be maintained. The study intervention will be

labeled according to the	labeled according to the
country's regulatory requirement	country's regulatory requirement

Abbreviations: CRU = clinical research unit; IMP = investigational medicinal product; NIMP = noninvestigational medicinal product.

